6.5.7.7. Pregnancy Reporting

If a female patient becomes pregnant during the study through 12 weeks following the last dose of study drug, the Investigator must report the pregnancy to the Sponsor or designee within 24 hours of being notified of the pregnancy. Details of the pregnancy will be recorded on the pregnancy reporting form. The patient should receive any necessary counseling regarding the risks of continuing the pregnancy, the possible effects on the fetus, and be counseled to not breastfeed for 12 weeks after the last dose of study drug.

The pregnancy should be followed by the Investigator until completion. At the completion of the pregnancy, the Investigator will document the outcome of the pregnancy. If the outcome of the pregnancy results in a postpartum complication, spontaneous abortion, stillbirth, neonatal death, or congenital anomaly, then the Investigator should follow the procedures for reporting an SAE as outlined in Section [6.5.7.4](#).

6.5.7.8. Overdose Reporting

An overdose is defined as any dose administered to or taken by a patient (accidentally or intentionally) that exceeds the highest daily dose, or is at a higher frequency, than included in the protocol. In the event of an overdose, the actual dose administered must be recorded as specified in the Pharmacy Manual.

All reports of overdose (with or without an AE) must be reported within 24 hours following the instructions outlined in the Pharmacy Manual for reporting an overdose.

6.6. Biomarkers and Biospecimen Repository

Alnylam's RNAi therapeutics platform permits the highly specific targeting of investigational therapies based on genetic sequence. It is possible that variations in the target genetic sequence will result in variations in drug effect. More generally, genetic variations may account for the well-described heterogeneous manifestations of disease in patients with ATTR amyloidosis with cardiomyopathy, as well as their responses to treatment.

Where allowed per local regulations, ethics committee (IRB/IEC) approval, and patient consent, samples will be collected as part of this study to permit exploratory investigations and the application of novel approaches to bioanalyses that may further elucidate the outcomes of this

study, or potentially advance understanding of the safety, mechanism of action, and/or efficacy of patisiran.

Biological specimens will be collected at the intervals indicated in the Schedule of Assessments ([Table 1](#) and [Table 2](#)). Potential exploratory investigations may include RNA, or biochemical metabolite assessments as they relate to disease progression, efficacy or safety.

The biospecimen repository will also include residual material from routine samples (safety laboratory samples, PK samples, etc.) that are obtained during the study.

These specimens will be securely stored in a central biorepository for up to 10 years following the completion of this clinical study (ie, last patient last visit), or as per local regulations. After 10 years have elapsed, samples will be destroyed.

Details regarding the collection, processing, storage, and shipping of the samples will be provided in the Laboratory Manual.

Exploratory analysis of these biospecimens will be performed by Alnylam Pharmaceuticals or its designees.

When biobanking is permitted by local regulation, study participants will be advised during the informed consent process of these biobanking details and the potential for exploratory investigation of their samples.

7. STATISTICS

A Statistical Analysis Plan (SAP) will be finalized before database lock. The plan will detail the implementation of the statistical analyses in accordance with the principal features stated in the protocol.

7.1. Determination of Sample Size

The planned enrollment for this study is 300 patients. For the change from baseline at Month 12 in the 6-MWT, assuming a treatment difference of 33 meters between patisiran and placebo in the treatment-naïve group and 20 meters in patients with baseline tafamidis, the weighted average treatment difference between patisiran and placebo in the overall population is approximately 29 meters (standard deviation = 75 meters) assuming 70% are in the treatment-naïve group and 30% are in the baseline tafamidis group. A sample size of 300 patients provides >90% power for a 2-sided test to detect a mean difference between treatment groups at a 2-sided alpha = 0.05. Additional patients may be enrolled based on a recommendation to increase the sample size in the interim assessment ([Section 7.2.10](#)).

7.2. Statistical Methodology

The statistical and analytical plans presented below are brief summaries of planned analyses for the primary analysis, conducted at the completion of the 12-month, double-blind period. More complete plans, including planned analyses for the open-label extension period, will be detailed in the SAP. Changes to the methods described in the final SAP will be described and justified as needed in the clinical study report. For information on study endpoints, see [Section 2](#).

7.2.1. Populations to be Analyzed

The populations (analysis sets) are defined as follows:

- Full Analysis Set (FAS): All randomized patients who received any amount of study drug, grouped according to the randomized treatment arm.
- Safety Analysis Set: All patients who received any amount of study drug, grouped according to the treatment actually received.
- PK Analysis Set: All patients who received any amount of study drug and have at least 1 postdose blood sample for PK parameters and have evaluable PK data.
- PD Analysis Set: All patients who received any amount of study drug and who have an evaluable baseline and at least 1 evaluable post-baseline serum TTR measurement will be included in the PD analyses.

Efficacy endpoints will be analyzed using the Full Analysis Set. Safety will be analyzed using the Safety Analysis Set. The PK and PD Analysis Sets will be used to conduct PK and PD analyses, respectively.

7.2.2. Examination of Subgroups

Subgroup analyses may be conducted for selected endpoints. Detailed methodology will be provided in the SAP.

7.2.3. Handling of Missing Data

Handling of missing data will be described in the SAP.

7.2.4. Baseline Evaluations

Demographics and other disease-specific baseline characteristics will be summarized by treatment arm and overall for the FAS and Safety Analysis Set.

7.2.5. Efficacy Analyses

The overall Type I error rate will be strongly controlled at a 2-sided 0.05 significance level for the primary and secondary endpoints using a fixed sequential testing procedure at the final analysis. The primary endpoint will be compared between treatment arms at the 0.05 significance level. If the test of the primary endpoint is statistically significant, then the secondary endpoints will each be tested in the order specified in the Secondary Endpoints section (see Section 2). If a test of the primary or a secondary endpoint is not statistically significant, the testing of the remaining endpoints in the sequence will stop.

For patients who were tafamidis treatment-naïve at baseline and start tafamidis during the double-blind period, the primary analysis of the primary endpoint will censor data collected after the initiation of tafamidis treatment post-randomization.

7.2.5.1. Primary Endpoint

The primary endpoint, change from baseline at Month 12 in the 6-MWT, will be analyzed using a mixed-effects model repeated measures (MMRM) approach. The outcome variable is change

from baseline in the 6-MWT. The model will include the baseline value as a covariate, treatment, visit, the treatment-by-visit interaction, baseline tafamidis (yes vs no), genotype (hATTR vs wtATTR), and age (<75 vs \geq 75 years) as fixed factors, and patient as a random effect. The primary comparison is the contrast (difference in least squares [LS] means) between the patisiran and placebo groups at Month 12.

Sensitivity analyses will be detailed in the SAP.

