3.5. Method of Assigning Patients to Treatment Groups

Using the interactive response system (IRS), patients will be randomized 1:1 to the patisiran or placebo arm. Randomization will be stratified by:

1. Baseline tafamidis (yes vs no)
2. Genotype (hATTR vs wtATTR amyloidosis with cardiomyopathy)
3. NYHA Class I or II **and** age < 75 years vs all other

Each patient will be uniquely identified in the study by a combination of the site number and patient identification number. Upon signing the informed consent form (ICF), the patient will be assigned a patient identification number by the IRS. The Investigator or his/her designee will contact the IRS to randomize the patient after confirming that the patient fulfills all the inclusion criteria and none of the exclusion criteria.

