7.2.5.2. Secondary Endpoints

Secondary endpoints are described in Section 2.

KCCQ-OS will be analyzed using a similar MMRM model as used for the primary endpoint.

The composite endpoint of all-cause mortality, frequency of CV-related hospitalizations and change from baseline in 6-MWT will be analyzed using a generalized rank-based win ratio method, which makes pairwise comparisons (for all possible patisiran/placebo patient pairs) of the 3 components in the hierarchical order specified above. The point estimate for the win ratio is defined as the total number of better outcomes divided by the total number of worse outcomes in the patisiran group. The detailed algorithm for assessment of this endpoint will be provided in the SAP.

The composite endpoint of all-cause mortality and all-cause hospitalizations will be analyzed using an Andersen-Gill model stratified by baseline tafamidis (yes vs no), including treatment, genotype (hATTR vs wtATTR), NYHA Class (I/II vs III), and age (<75 vs \geq 75 years) as covariates.

Patients who undergo a heart transplantation and/or ventricular assist device placement after randomization will be handled in the same manner as death in the primary analyses of mortality related endpoints.

To control the overall Type I error rate, secondary endpoints will be tested in a prespecified hierarchical order.

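### The primary MMRM leaves out the joint NYHA/age randomisation factor, and the win ratio as described is unstratified: no bias, a small loss of efficiency, cheap to repair

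*Protocol*

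**What the plan says.** **Randomisation.** Section 3.5 of the Protocol allocates 1:1 within strata formed by baseline tafamidis, genotype and one binary joint factor: "NYHA Class I or II and age < 75 years vs all other".

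**Primary analysis.** Section 7.2.5.1 specifies: "The model will include the baseline value as a covariate, treatment, visit, the treatment-by-visit interaction, baseline tafamidis (yes vs no), genotype (hATTR vs wtATTR". The sentence then adds age (under 75 against 75 and over) as a fixed factor and patient as a random effect. So the model holds two of the three randomisation factors, the age half of the third at the same cut, and continuous baseline 6-MWT. It does not hold NYHA class or the joint factor.

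**Why NYHA is absent.** The Amendment 1 summary of changes explains that NYHA was taken out because it correlates with baseline 6-MWT, which stays in, and because a more parsimonious model was wanted. It does not mention that NYHA helps to define a randomisation factor.

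**Secondary analyses.** Section 7.2.5.2 gives KCCQ-OS an MMRM like the primary one. It describes the win ratio as a method "which makes pairwise comparisons (for all possible patisiran/placebo patient pairs) of the 3 components in the hierarchical order specified above", estimated as total better over total worse outcomes, and leaves the detailed algorithm to the SAP. The Andersen-Gill analysis of the other composite is stratified by baseline tafamidis, with genotype, NYHA and age as covariates.

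This is the Amendment 1 text. The Amendment 2 summary revises the components of the composites but lists no change to the MMRM factors or to the pairing.

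**The concern.** Stratified randomisation balances the arms on the stratifying factors. If such a factor predicts outcome and is left out of the analysis, the model still counts the variation it explains as noise. The reported standard error is then somewhat too large, the test becomes conservative, and some of the precision gained by stratifying is not used.

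Age alone cannot rebuild the joint factor. A NYHA III patient under 75 is randomised with the remainder group, yet shares a model level with NYHA I/II patients under 75. The reason given for dropping NYHA is also specific to the walk test. If the KCCQ-OS model uses its own baseline score, baseline 6-MWT is not there to stand in for NYHA, and the win ratio as described has no covariates at all.

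The win ratio text uses none of the three strata, although Section 7.1 expects the treatment effect to differ by tafamidis status. Two composites in the same fixed testing sequence are therefore handled differently without explanation. What is at stake is efficiency and consistency, not validity.

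**Working it through.** **Inputs from Protocol Section 7.1:** "assuming a treatment difference of 33 meters between patisiran and placebo in the treatment-naïve group and 20 meters in patients with baseline tafamidis"; "assuming 70% are in the treatment-naïve group and 30% are in the baseline tafamidis group"; an overall difference of "approximately 29 meters (standard deviation = 75 meters"); "A sample size of 300 patients provides >90% power for a 2-sided test"; "at a 2-sided alpha = 0.05". Allocation is 1:1 (Section 3.5), so 150 per arm.

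**1. The plan's own figure.**
- Weighted effect: 0.7 × 33 + 0.3 × 20 = 23.1 + 6.0 = 29.1 m.
- SE = 75 × √(2/150) = 8.66 m; 29/8.66 = 3.35.
- Power = Φ(3.35 − 1.96) = 91.8% (noncentral t on 298 df: 91.6%; with 29.1 m: 91.9%).

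The stated power reproduces. For 90%, 141 per arm (282 in total) would be enough, with no allowance for dropout.

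**2. Leaving the joint factor out.** Let R² be the share of the 75 m residual variance that the factor explains. The documents give no value, so 0 to 10% is an assumed range.
- With the factor in the model: SD = 75 × √(1 − R²), tested at 1.96.
- Without it, under stratified randomisation: the estimate has the smaller variance but is judged by the larger SE, so the effective critical value is 1.96/√(1 − R²).
- True alpha = 2 × [1 − Φ(1.96/√(1 − R²))].
- SE overstatement = 1/√(1 − R²) − 1.

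| R² (assumed) | SE overstated | True alpha, factor omitted | Power, factor omitted | Power, factor included | Loss (points) |
|---|---|---|---|---|---|
| 0% | 0% | 5.00% | 91.75% | 91.75% | 0 |
| 1% | 0.5% | 4.89% | 91.86% | 92.01% | 0.15 |
| 2% | 1.0% | 4.77% | 91.97% | 92.26% | 0.29 |
| 5% | 2.6% | 4.43% | 92.29% | 93.00% | 0.71 |
| 10% | 5.4% | 3.88% | 92.84% | 94.18% | 1.34 |

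Age at the same cut is already in the model, so part of what the joint factor explains has been removed. With R² read as the factor's whole share, the table is an upper bound.

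**3. Simulation check.** Trials of 300 patients, blocks of 4 within eight strata, 30% on tafamidis, 20% hATTR. Assumed: 50% aged 75 or over, 20% NYHA III, NYHA effect −25 or −50 m, residual SD 75 m. A single-visit regression on treatment, tafamidis, genotype and age stands in for the MMRM; baseline 6-MWT was not simulated. There were 6,000 trials per setting, so the Monte Carlo SE at 5% is √(0.05 × 0.95/6000) = 0.3 points.

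| NYHA effect | Null rejection, current / factor added | Power at 29 m, current / factor added |
|---|---|---|
| −25 m | 4.9% / 4.8% | 90.6% / 90.7% |
| −50 m | 5.2% / 5.2% | 89.7% / 90.6% |

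Type I error stays at 5% within simulation error. The power loss is between 0 and 0.9 points.

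**4. Win ratio.** An all-pairs rank comparison against a stratified one, on the 6-MWT component only (4,000 trials per setting), gave null rejection of 4.5% / 4.3% (all pairs, NYHA −25 / −50 m) against 4.5% / 4.6% (stratified). Power was 89.3% / 88.9% against 89.1% / 89.2%, so the sign of the difference varies. A separate simulation of 1,500 trials with strongly prognostic strata (assumed effects) gave type I error of 4.0% for all pairs against 5.0% stratified, and power of 57% against 60%. With weakly prognostic strata there was no difference.

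**The case against.** The best defence is that the omission was deliberate and reasoned. NYHA overlaps with baseline 6-MWT, which the model keeps, and Amendment 1 says so. The Andersen-Gill model lists no baseline 6-MWT, so keeping NYHA there fits the same reasoning; it also enters NYHA and age separately, not as the joint factor. This largely explains the difference between those two models and supports the small effect found. It does not deal with NYHA's role in randomisation, and it does not clearly carry over to KCCQ-OS or to the win ratio.

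A reader might infer that both analyses ignore the randomisation strata. For the MMRM that is wrong: tafamidis, genotype and age at the 75-year cut are all present, and only the NYHA part of the joint factor is missing.

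A reader might also infer that cross-stratum pairs bias the win ratio, since prognosis decides many of them. Under 1:1 stratified randomisation those wins and losses balance in expectation, so there is no bias.

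Finally, the SAP is to supply the detailed win ratio algorithm and could stratify it. That stands in part: the pairing and the pooled estimator are already stated in the Protocol, and Section 7 requires the SAP to follow its principal features, but the text shows an analysis not stratified as described, not a settled defect.

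**Conclusion.** The point holds as a minor one. The MMRM omits the joint NYHA/age factor that the trial randomises by, for a reason that does not consider randomisation. The win ratio is described without strata, unlike the model beside it. There is no bias and no inflation of type I error. The primary test may be slightly conservative (true alpha between 3.9% and 5.0% by formula; no departure from 5% seen in simulation) and may lose about 0 to 1.3 power points.

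These sizes rest on an assumed R² of 0 to 10%, an upper bound because age is already adjusted for. The win ratio effect depends on how prognostic the strata are, from nothing to about 3 points under strong assumed effects. The documents do not support calling the test invalid or the power claim wrong, since the stated power reproduces. The statistics section as revised by Amendment 2 was not available in full, so persistence of the wording is inferred from that amendment's summary listing no relevant change.

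**What to change.** - **MMRMs for 6-MWT and KCCQ-OS (Sections 7.2.5.1 and 7.2.5.2):** add the joint NYHA/age factor exactly as used in the randomisation. Keep age as it is. Substituting the joint factor for age would pool NYHA I/II patients aged 75 and over with NYHA III patients and drop a planned covariate; the calculations above cover only addition.
- **Win ratio (Section 7.2.5.2):** form pairs within strata defined at least by baseline tafamidis, and combine the within-stratum wins and losses with stated weights. Avoid splitting into sparse genotype cells: with 20% hATTR and up to 30% on tafamidis, independence would leave only 300 × 0.20 × 0.30 = 18 patients in that cell before any NYHA/age split.

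The cost is a wording change in two sections, about one degree of freedom in each MMRM, and fewer pairs in the win ratio. The sample size and the alpha level do not change.

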To evaluate the efficacy of treatment with patisiran versus placebo in patients with ATTR amyloidosis with cardiomyopathy, the change from baseline in 6-MWT will be assessed at Month 12 (Weeks 52-53) as the primary endpoint (Section 2); this assessment will also be performed at Month 6 (Weeks 25-26) and Month 9 (Weeks 37-38) in the double-blind period, and during the open-label extension period at the time points noted in the Schedule of Assessments (Table 1 and Table 2). The first secondary endpoint will assess change from baseline at Month 12 in the KCCQ-OS score.

Safety will be assessed throughout the study, as described in the Schedule of Assessments for the double-blind period (Table 1) and for the open-label extension period (Table 2).

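### The primary 6-MWT model fits one baseline slope to Months 6, 9 and 12; a baseline-by-visit term would be a cheap, minor safeguard for the Month 12 contrast

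*Protocol*

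**What the plan says.** Protocol Section 7.2.5.1 gives the mean model for change in 6-MWT term by term: "The model will include the baseline value as a covariate, treatment, visit, the treatment-by-visit interaction". It adds baseline tafamidis, genotype and age group "as fixed factors, and patient as a random effect". The Synopsis repeats the list. No baseline-by-visit interaction appears in either place.

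The test is at one visit: "The primary comparison is the contrast (difference in least squares [LS] means) between the patisiran and placebo groups at Month 12". The other post-baseline assessments in the model are at "Month 6 (Weeks 25-26) and Month 9 (Weeks 37-38) in the double-blind period". For the first secondary endpoint, Section 7.2.5.2 says: "KCCQ-OS will be analyzed using a similar MMRM model as used for the primary endpoint".

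Section 7.2.5 censors 6-MWT data collected after a tafamidis-naïve patient starts tafamidis. Section 7.2.3 leaves the handling of missing data to the SAP.

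**The concern.** With baseline as a main effect only, the model assumes that a given difference in baseline walk predicts the same difference in change at every visit. The disease is progressive, and Section 1.1 describes decline that is measurable within 12 months, so a constant relation is an untested assumption. If it fails, the fitted slope is a compromise across visits and Month 12 is adjusted with a slope that is not its own.

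Two things could follow. Baseline variation that should have been removed stays in the Month 12 residual and widens the standard error. And if the patients still observed at Month 12 differ in baseline walk between arms, the misfit no longer cancels and the contrast shifts. Tafamidis censoring is one possible route: under Section 5.3.1 the start of tafamidis rests on the investigator's judgement, which may follow severity or how the patient is faring.

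Baseline 6-MWT also carries more of the severity adjustment since Amendment 1, which removed NYHA class from the model because it correlates with baseline walk.

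**Working it through.** **Inputs from the Protocol.** Section 7.1: "assuming a treatment difference of 33 meters between patisiran and placebo in the treatment-naïve group and 20 meters in patients with baseline tafamidis"; overall, "approximately 29 meters (standard deviation = 75 meters) assuming 70% are in the treatment-naïve group and 30% are in the baseline tafamidis group"; and "A sample size of 300 patients provides >90% power for a 2-sided test" at alpha 0.05. Section 3.5: 1:1 allocation, so 150 per arm.

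**Inputs assumed, because the Protocol gives none.** Baseline 6-MWT SD of 80-120 m (100 m in the simulations); SDs of change at Months 6 and 9 of 55-60 m and 65-68 m; between-visit correlations of 0.5-0.7; the baseline slopes; and Month 12 dropout of about 13-15%. The 75 m is taken as the Month 12 residual SD when the baseline slope at that visit is right.

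**The plan's own figure.** Weighted effect: 0.7 × 33 + 0.3 × 20 = 29.1 m. SE = 75 × √(2/150) = 8.66 m. Power = Φ(29/8.66 − 1.96) = Φ(1.389) = 91.8% (91.6% with the noncentral t). The claim of more than 90% is reproduced.

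**Precision by formula.** Let the gap be the Month 12 slope minus the fitted common slope. The residual variance rises by (gap × baseline SD)², so the SE is multiplied by √(1 + (gap × baseline SD)²/75²). For a gap of 0.10 and a baseline SD of 100 m: √(1 + 100/5625) = 1.009.

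| Gap | Baseline SD 80 m | 100 m | 120 m |
|---|---|---|---|
| 0.05 | SE × 1.001, power 91.7% | 1.002, 91.6% | 1.003, 91.6% |
| 0.10 | 1.006, 91.5% | 1.009, 91.3% | 1.013, 91.1% |
| 0.15 | 1.013, 91.1% | 1.020, 90.7% | 1.028, 90.3% |
| 0.20 | 1.022, 90.6% | 1.035, 89.9% | 1.050, 89.1% |

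The gap is not the same as the shift from Month 6 to Month 12. With evenly spaced slopes and equal weight on the three visits, which is what a random intercept gives with complete data, the gap is half the shift. A shift of 0.10 then costs 25/5625 = 0.4% of variance, and 0.20 costs 100/5625 = 1.8%.

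**Precision by simulation.** 300 patients, complete data, unstructured covariance, baseline SD 100 m:

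- Slopes −0.10/−0.15/−0.20 (shift 0.10): mean SE 8.68 with a common slope and 8.63 by visit; (8.68/8.63)² = 1.012.
- Slopes −0.05/−0.15/−0.25 (shift 0.20): 8.80 and 8.63; (8.80/8.63)² = 1.040.
- Other assumed visit SDs and correlations: the interaction saves 0.5-0.6% of variance at a shift of 0.05, 0.1-3.1% at 0.10 and 5.3-5.9% at 0.20.
- Equal slopes: the interaction costs 0.3-0.5% of variance in one set of simulations and nothing measurable in another (SE 8.60 for both models).

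The largest saving found, a variance ratio of 0.941, means that the common-slope SE is larger by √(1/0.941) = 1.031. Power is then Φ(29/(8.66 × 1.031) − 1.96) = Φ(1.288), about 90.1%.

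**Bias.** Limiting error of the Month 12 contrast with 400,000 simulated patients and 13-14% dropout (Monte Carlo SE about 0.24 m), unstructured covariance:

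| How dropout depends on baseline | Shift 0.10: common / by visit | Shift 0.20: common / by visit |
|---|---|---|
| Same in both arms | +0.08 / +0.02 m | 0.00 / +0.05 m |
| Placebo arm only | +1.03 / +0.14 m | +2.10 / +0.32 m |
| Opposite directions | +1.88 / +0.08 m | +3.19 / −0.30 m |

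A compound-symmetry covariance gives nearly the same values (for example +0.96 and +1.97 m for placebo only). Milder arm-unequal dropout of about 15% moved the contrast by 0.2-0.9 m. With truly equal slopes, neither model was biased under any dropout pattern. The positive sign reflects the scenarios chosen.

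**The case against.** **A valid model without an optional term.** Every quantity behind the harm is assumed; the Protocol reports no visit-specific slopes, baseline SD or dropout rate. This stands. It limits the point to a recommended improvement.

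**SAP detail.** Section 7.2 calls these plans summaries to be completed in the SAP, which is not at hand. But Section 7 binds the SAP to the principal features stated in the Protocol. A list of fixed terms that names one interaction and not the other reads as such a feature. Section 7.2.5.1 itself defers only sensitivity analyses.

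**Version.** The section examined is from the Amendment 1 protocol body. The Amendment 2 summary of changes lists an edit to Section 7.2.5.2 and none to 7.2.5.1, so the model was probably carried forward, but later protocol text was not seen. This stands as a condition on the fix.

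**Early visits dominating.** A reader might infer that the less variable early visits pull the common slope toward themselves. That needs an unstructured covariance with smaller early SDs. The Protocol names only a random patient effect, and read literally that weights the visits equally with complete data. The averaging remains, but the early-visit dominance is not supported by the text.

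**KCCQ-OS.** The Protocol says only that the model is similar, so the point carries over only if the same terms are used.

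**Conclusion.** The reading of the model holds: one baseline slope is imposed on three visits while one visit is tested. The consequence is conditional and small.

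- **Precision.** It is lost only if the slopes truly differ by visit: about 0-3% of Month 12 variance at a shift of 0.05-0.10 and about 2-6% at 0.20, for an assumed baseline SD of 100 m. The lower end at 0.20 belongs to a random intercept and the upper end to an unstructured covariance.
- **Bias.** It needs slopes that differ by visit and, in addition, dropout or tafamidis censoring that relates to baseline differently by arm. It is then roughly 0.2-3 m, which is 0.7-10% of the planned 29 m (0.2/29 and 3/29) and at most about a third of the standard error (3/8.66 = 0.35).

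Two stronger readings are tempting. One is that any baseline-dependent dropout biases the result. It does not: dependence that is equal in both arms gave 0.00 to 0.08 m, within simulation error. The other is that the primary analysis or the sample size fails. In the formula, power drops below 90% only at a gap of 0.20 with a baseline SD of 100 m or more, and at a shift of 0.20 with a baseline SD of 100 m even the largest simulated loss left about 90.1%. This is a minor, inexpensive improvement.

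**What to change.** Confirm the wording of Section 7.2.5.1 and the Synopsis in the current protocol version and in the SAP. If the interaction is absent, add baseline 6-MWT-by-visit to the primary model, and baseline KCCQ-OS-by-visit to the KCCQ-OS model.

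The cost is one term per model. With three visits that is 3 − 1 = 2 degrees of freedom, at most about 0.3-0.5% of variance if the slopes are equal. No extra patients, visits or data are needed. The change should be made before unblinding.
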